# 10.7 Pregnancy Testing

Pregnancy tests for females of childbearing potential. A female of childbearing potential (FCBP) is a sexually mature female who: 1) has not undergone a hysterectomy or bilateral oophorectomy; or 2) has not been naturally postmenopausal for at least 24 consecutive months (i.e. has had menses at any time in the preceding 24 consecutive months).

Pregnancy tests will be required by the Revlimid REMS® program and will occur within 10-14 days and again within 24 hours prior to prescribing lenalidomide for Cycle 1 (prescriptions must be filled within 7 days). FCBP with regular or no menstruation must have a pregnancy test weekly for the first 28 days and then every 28 days while on therapy (including breaks in therapy); at discontinuation of lenalidomide and at Day 28 post the last dose of lenalidomide. Females with irregular menstruation must have a pregnancy test weekly for the first 28 days and then every 14 days while on therapy (including breaks in therapy), at discontinuation of lenalidomide and at Day 14 and Day 28 post the last dose of lenalidomide (see Appendix A: Risks of Fetal Exposure, Pregnancy Testi ng Guidelines and Acceptable Birth Control Methods).

## 10.8 Follow-Up

Patients, who discontinue treatment for any reason, will be followed for 1 month or until resolution of all treatment related AEs or initiation of alternate cancer therapy, whichever is longer. At treatment discontinuation, patients will undergo a safety assessment approximately 1 month after the last dose of protocol therapy. In addition, off study evaluations per the end of study assessments will be done.

## 11.0 TOXICITIES/SIDE EFFECTS

## Side Effects of Romidepsin

#### Likely

- Nausea
- Vomiting
- · Loss of appetite
- Fatigue
- Constipation
- Diarrhea
- Altered sensation of taste
- Fever

#### Side effects related to levels of substances found in the blood:

- Thrombocytopenia
- Anemia
- Leukopenia
- Hyperglycemia
- Hypocalcemia
- Hypomagnesemia
- Hypoalbuminemia

# **Less Likely**

- Swelling
- Decreased weight
- Heart tracing irregularities
- Weakness
- Joint pain
- Itching
- Back pain
- Dizziness
- Abdominal pain
- Dehydration
- Changes in heart function
- Heartburn
- Low blood pressure
- Cough
- Skin infections
- Shortness of breath
- Headache
- Feeling of discomfort or uneasiness
- Insomnia
- Burning or tingling sensations
- Headache
- Feeling of discomfort or uneasiness

## Side effects related to levels of substances found in the blood:

- Hyperbilirubinemia
- Hypokalemia
- Lymphopenia
- Hyponatremia
- Hypermagnesemia
- Increased creatinine
- Hypophosphatemia
- Elevated transaminases
- Elevated alkaline phosphatase

# Rare but serious

- Anxiety
- Infections
- Bleeding
- Increased heart rate
- Hyperkalemia
- Hyperuricemia
- Pancreatitis
- Deep venous thrombosis
- Syncope

## Side Effects of Lenalidomide

#### Likely:

- Fatigue or feeling tired
- Lack or loss of strength
- Anemia or a decrease in red blood cells that can cause tiredness
- Decrease in white blood cells that can make you more prone to infections (Neutropenia)
- Decrease in platelets which can cause you to bruise or bleed easily (Thrombocytopenia)
- Blood clot in lower extremities
- Vision blurred
- Nosebleed
- Constipation or difficulty moving your bowels
- Diarrhea or loose/frequent bowel movements
- Nausea or vomiting
- Loss of appetite
- Joint pain
- Swelling of the arms and legs
- Fever
- Cough

- Shortness of breath or difficulty catching your breath
- Upper respiratory infection (infection of nose, sinus, and throat)
- Allergic reaction
- Itching and dry skin
- Dizziness
- Headache
- Altered sense of taste
- Abnormal sense of touch
- Pain and decreased sensation in nerves
- Pneumonia

#### Less Likely:

- Problem with moving food through digestive system (gastrointestinal motility disorder)
- Dry mouth
- Indigestion (dyspepsia)
- Muscular weakness
- Stroke
- Tingling sensation (paresthesia)
- Fainting (syncope)
- Drowsiness
- Difficulty breathing (respiratory distress)
- Excessive sweating (hyperhidrosis)
- Fever with a decrease in white blood cells that help fight infections (febrile neutropenia)
- Shortage of all types of blood cells including red blood cells, white blood cells, and platelets (pancytopenia)
- Excessive loss of body water (dehydration)
- High blood sugar (hyperglycemia)
- Uncontrolled blood sugar (diabetes mellitus)
- Higher than normal blood uric acid (hyperuricemia)
- Higher than normal level of iron in body (iron overload)
- Lens of eye becomes cloudy (cataracts)
- High blood pressure (hypertension)
- Low blood pressure (hypotension)
- Bleeding
- Altered mood
- Depression
- Irregular heartbeat (atrial fibrillation)
- Failure of the heart (cardiac failure)
- Heart attack (acute myocardial infarction)
- Fast heartbeat (tachycardia)
- Not enough blood flow to heart muscle (myocardial ischemia)
- Secondary cancer
- Kidney damage (renal failure)

- Abnormal liver function tests
- Tumor lysis syndrome

#### Rare but Serious

- Fever with a decrease in white blood cells that help fight infections (Febrile neutropenia)
- Blood clot in or around the lungs (Pulmonary embolism)
- Deep vein thrombosis or blood clots in larger blood vessels
- Atrial fibrillation or irregular heartbeat
- Pneumonia or an infection of the lungs
- Sepsis or an infection of the blood
- Kidney failure or inability of the kidneys to remove waste from the body
- Muscle breakdown (rhabdomyolysis)
- Swelling of the lungs
- Severe skin rash (Stevens-Johnson syndrome)

# Side Effects of Carfilzomib

#### **Likely Side Effects:**

- Fatigue (tiredness)
- Fever
- Headache
- Cough
- Cough with phlegm
- Shortness of breath (at rest or with exertion)
- Nausea
- Vomiting
- Diarrhea
- Constipation
- Decreased red blood cell count which may lead to feeling tired
- Decreased platelet counts which may lead to increase bleeding or bruising
- Decreased white blood cell count
- Upper respiratory tract infection
- Mild decreases in kidney function which are generally reversible
- Swelling of the arms or legs
- Back pain
- High blood pressure
- Pneumonia or other lower respiratory tract infections

## **Less Likely Side Effects:**

- Flu-like symptoms such as fever, chills, or shaking that may occur at any time but are more likely to occur on the day of or the day after carfilzomib infusion.
- Loss of or decreased appetite which may lead to weight loss

- Insomnia (difficulty sleeping)
- Anxiety
- Dizziness
- Confusion or changes in mental state
- Blurred or double vision
- Numbness, tingling, or decreased sensation in hands and/or feet
- Blood chemistry and electrolyte alterations
- Rash and/or itching, or dry skin
- Pain, burning, or irritation at the infusion site
- Generalized pain
- Pain in the bones or joint pain
- Muscle spasm, pain, or weakness
- General weakness, or lack of energy or strength
- Abdominal pain, discomfort, or swelling
- Indigestion (upset stomach)
- Inflammation of the liver (mild, reversible changes in liver function tests)
- Increase or decrease in blood pressure
- Urinary tract infection
- Nosebleeds
- Dehydration
- Sore throat, inflammation of the nose and throat, runny nose or nasal congestion
- Blood clots in the leg or lungs
- Change in voice or hoarseness
- Toothache
- Low white blood cell count which may be associated with fever
- Low blood pressure

#### Rare and/or Potentially Serious Side Effects:

- Infusion reactions (which can occur during or shortly after carfilzomib infusion)
  including flushing or feeling hot, fever, shakes, nausea, vomiting, weakness,
  shortness of breath, swelling of the face, pain in the muscles or joints, tightness or
  pain in the chest, and low blood pressure
- Allergic reaction including total body rash, hives, and difficulty breathing
- Inflammation of the pancreas (pancreatitis)
- Kidney failure which can lead to dialysis
- Worsening liver function up to and including liver failure
- Decreased or worsening of heart function including chest pain, abnormal heart rhythm, heart attack, and heart failure
- Severe shortness of breath leading to hospitalization or death
- Increase in the blood pressure in the arteries of the lungs
- Infections in the blood
- Thrombotic thrombocytopenic purpura (TTP)
  - TTP is a rare blood disorder. In TTP, blood clots form in small blood vessels throughout the body. The clots can limit or block the flow of

oxygen-rich blood to the body's organs, such as the brain, kidneys, and heart.

- Hemolytic-uremic syndrome (HUS)
  - HUS is a disorder that usually occurs when an infection in the digestive system produces toxic substances that destroy red blood cells, causing kidney injury.
- Secondary cancers such as myelodysplastic syndrome (MDS) / Acute Myeloid Leukemia
  - Myelodysplastic syndromes refers to disorders that develop when the cells in the bone marrow (the soft inner part of the bones, where new blood cells are made) do not work properly and have problems making new blood cells.
- Posterior Reversible Encephalopathy Syndrome (PRES)
  - PRES is a rare, neurological disorder, which can present with seizure, headache, lethargy, confusion, blindness, altered consciousness, and other visual and neurological disturbances, along with hypertension.
- Tumor lysis syndrome (TLS)
  - Tumor lysis syndrome is caused by rapid killing of tumor cells during treatment. When the tumor cells die, they release their contents into the bloodstream. If cell killing is very rapid, this can affect blood chemistries and the kidneys. In severe cases, this can lead to shutdown of kidney function requiring dialysis.
- Pulmonary hemorrhage (bleeding in the lungs)
- Brain Hemorrhage
- Bleeding in the stomach and bowels

# 12.1 CRITERIA FOR THERAPEUTIC RESPONSE/OUTCOME ASSESSMENT

Response and progression of disease will be evaluated in this study using a modification of the international criteria proposed by the modified Cheson criteria with incorporation of PET/CT. [Cheson B, 2007]. The imaging modality for evaluation will be dependent on disease subtype. For aggressive lymphomas (e.g. DLBCL, PTCL, HL), PET/CT will be used for evaluation of response. For indolent lymphomas, CT alone or PET/CT may be used at the discretion of the treating physician. For CTCL, please see Section 12.0.2.

Measurable disease: Measurable lesions are defined as those that can be accurately measured in at least one dimension (longest diameter to be recorded) as  $\geq$  15 mm with conventional techniques (PET, CT, MRI, x-ray). All tumor measurements must be recorded in millimeters (or decimal fractions of centimeters).

Non-measurable disease: All other lesions (or sites of disease), including small lesions (longest diameter < 15 mm), are considered non-measurable disease. Bone lesions, leptomeningeal disease, ascites, pleural/pericardial effusions, lymphoma

Memorial Sloan Kettering Cancer Center IRB Number: 14-179 A(6)
Approval date: 12-Dec-2017

Administrative Update 1 : 06-Dec-2018

cutis/pulmonis, inflammatory breast disease, abdominal masses (not followed by CT or MRI), and cystic lesions are all non-measurable.

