# 6.1 CRITERIA FOR SUBJECT ELIGIBILITY

# 6.2 Subject Inclusion Criteria

- a) Pathologically confirmed B- or T-cell lymphomas at the enrolling institution, including stage ≥ lb CTCL, which has relapsed or progressed after at least one systemic therapy.
  - Hodgkin lymphoma is allowed and will be classified as a B-cell lymphoma in the phase IIA portion.
- b) Age ≥ 18,
- c) Previous systemic anti-cancer therapy must have been discontinued at least 3 weeks prior to treatment and adverse effects must have resolved to ≤Grade 1 or baseline. In the phase Ila portion, in progressing subjects a 2 week washout may be allowed after discussion with the MSK Principal Investigator.
- d) Previous radiation, hormonal therapy, and/or surgery must have been discontinued or completed at least 2 weeks prior to treatment in this study and adverse effects must have resolved. Lymph node or other diagnostic biopsies within 2 weeks are not considered exclusionary.
- e) ECOG≤2
- f) Meet the following laboratory criteria:
  - Absolute neutrophil count ≥ 1.0/mm³,
  - Platelet count ≥ 80 K/μ (in the Phase IIa portion, if thrombocytopenia is due to bone marrow involvement platelet count must be ≥ 50 K/μL),
  - Phase Ib subjects must have calculated creatinine clearance ≥ 50ml/min by Cockcroft-Gault formula, phase IIa subjects must have calculated creatinine clearance ≥ 40ml4/min by Cockcroft-Gault formula.
  - Total bilirubin ≤ 1.5 x upper limit of normal (ULN). AST (SGOT) and ALT (SGPT) ≤ 3 x ULN.
- g) Measurable disease for phase IIa portion only.
  - Lymphoma (includes CTCL patients who are without evidence of the disease in the skin): CT or PET/CT by modified Cheson criteria with incorporation of PET.
  - CTCL: mSWAT >0, or absolute Sezary count ≥ 1000 cells/μL.

- h) All study participants must be registered into the mandatory Revlimid REMS® program, and be willing and able to comply with the requirements of the REMS® program.
- i) Short course systemic corticosteroids for disease control, improvement of performance status or non-cancer indication (≤ 7 days) must have been discontinued at least 6 days prior to study treatment. Stable ongoing corticosteroid use (≥ 30 days) up to an equivalent dose of 15 mg of prednisone is permissible.
  - Topical steroids that have been used for > 3 weeks may be continued (CTCL only).

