#### 8.1 PRETREATMENT EVALUATION

# 8.2 Documentation of tests resulted and/or verification to be performed within 28 days of starting treatment.

- 1. Record prior medications and treatments
- 2. Record prior anti-cancer therapy
- 3. Physical examination
- 4. ECOG performance status
- 5. 12 lead ECG
- 6. ECHO or Cardiac MRI
- 7. Complete metabolic panel, including magnesium and phosphorus
- 8. Lactate dehydrogenase (LDH)
- 9. PET/CT or CT Chest, Abdomen, and Pelvis
- 10. Register patient with Revlimid REMS® program.

- 11. mSWAT for patient with cutaneous lymphoma.
- 12. Sezary panel in patients with Sezary syndrome only.
  - Sezary panel: peripheral blood flow cytometry including CD2, CD3, CD4, CD8, CD26 and or CD7
- 13. Phase IIa only: patients with suspected or known prior bone marrow involvement must have a bone marrow biopsy performed.
- 14. Pregnancy testing for females of childbearing potential within 10-14 days and again 24 hours prior to prescribing lenalidomide per the Revlimid REMS® program.

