# Complete Remission (CR):

- No clinical, radiographic or diagnostic evidence of disease.
- No disease related symptoms.
- Abnormal biochemical values (e.g., LDH) clearly attributable to lymphoma must have normalized.
- Lymph nodes, nodal masses regressed to "normal" size:
- If > 1.5 cm before treatment regressed to  $\leq$  1.5 cm in GTD.
- If 1.1 to 1.5 cm before treatment, regressed to ≤ 1 cm in GTD (or >75% in SPD).
- Spleen and all previously enlarged organs decreased in size. Spleen must not be palpable on exam
- Bone marrow free of disease on repeat aspirate and biopsy if initially positive.
- Normalization of PET scan.

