# Complete Remission/unconfirmed (CRU):

Patients meeting the above criteria for CR with the following exceptions:

- Residual node mass of >1.5 cm in GTD regressed by > 75% in SPD.
- Individual nodes previously confluent regressed by >75% in SPD
- Indeterminate bone marrow (increased number or size of lymphoid aggregates without cytologic or architectural atypia).

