#### PET negative Partial Remission (PET-PR):

 Patient meets above criteria for PR with resolution of previous PET positive lesions.

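### CR and CRu require a normal PET without exception, yet indolent lymphomas may be assessed by CT alone, so as written a CT-only patient whose disease has fully resolved cannot be counted as a complete response

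*Combined protocol and SAP*

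**What the plan says.** Section 12.1 sets the response scan by subtype. For aggressive disease it is fixed: "For aggressive lymphomas (e.g. DLBCL, PTCL, HL), PET/CT will be used for evaluation of response". For indolent disease it is not: "For indolent lymphomas, CT alone or PET/CT may be used at the discretion of the treating physician". Footnote 7 to the study calendar (Appendix G) repeats both rules.

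Section 12.1.1 then defines the categories. Among the items for complete remission is "Normalization of PET scan", with no condition attached. The marrow item in the same list does carry one: "Bone marrow free of disease on repeat aspirate and biopsy if initially positive". CRu is defined as "Patients meeting the above criteria for CR with the following exceptions", and three exceptions follow: a residual nodal mass, previously confluent nodes, and an indeterminate marrow. PET is not among them. PET-negative PR is defined as "Patient meets above criteria for PR with resolution of previous PET positive lesions".

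At entry, Section 8.2 item 9 accepts "PET/CT or CT Chest, Abdomen, and Pelvis" for every patient, and Section 6.2(g) accepts "CT or PET/CT by modified Cheson criteria with incorporation of PET" for measurable disease in phase IIa.

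CR and PR rates are secondary endpoints (Section 2.1). Section 14.0 reports them as proportions with confidence intervals and describes efficacy as descriptive. Phase IIa is planned for 20 patients, 10 B-cell and 10 T-cell (Sections 4.2 and 9.3).

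**The concern.** The imaging rule allows a route of assessment that the response definitions do not provide for. A patient followed by CT alone has no PET to normalize. Two people applying the protocol in good faith could then put the same patient in different categories, one holding to the list as written and the other passing over an item that cannot be assessed.

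At stake is the split between CR and PR, which is a reported endpoint and part of the background for a later subtype-specific study. The choice of scan rests with the treating physician, the study is open label, and patients come from two centers that could settle the question differently. Nothing in Section 12.1 or Appendix G requires an indolent patient to keep the same modality from one assessment to the next.

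**Working it through.** The plan states no figure that depends on this rule, so there is none to reproduce. The check is a reading of the text, followed by simple arithmetic on its effect.

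**Step 1. Can a CT-only patient satisfy CR?** The PET item has no qualifier such as *if performed* or *if initially positive*. The marrow item shows that the authors wrote a condition where they wanted one. Read literally, the answer is no.

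**Step 2. Can the patient satisfy CRu?** CRu takes all CR items except three, and PET is not one of the three. The answer is again no.

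**Step 3. Where does the patient go?** PR does not need PET. A patient whose nodes have resolved would ordinarily meet the 50% reduction in the sum of products, so the literal result is PR at best.

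**Step 4. What if the PET item is waived?** The patient is CR on the remaining items: no clinical, radiographic or diagnostic evidence of disease, no disease-related symptoms, normalized laboratory values, node size, spleen and other organs, and marrow if it was involved.

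**Step 5. Which endpoints change?** From the definitions in Section 4.2:
- ORR counts CR, CRu and PR together, so moving a patient between CR and PR leaves it unchanged.
- TTR ends, and DOR starts, at the first response of any of these kinds.
- EFS ends at progression, change of therapy or death and does not use the response category.
- The CR and PR rates do change.

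**Step 6. By how much?** Let *b* be the number of other CRs among the 20 and *m* the number of CT-only indolent patients with fully resolved disease. The CR rate is *b*/20 with the PET item applied and (*b* + *m*)/20 with it waived. The difference is *m*/20, or 5 points per patient. The PR rate falls by the same amount if all *m* would otherwise be PR.

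The documents give neither *b* nor *m*. As an illustration only, assume *b* = 2 and let *m* run from 1 to 5 (exact Clopper-Pearson 95% intervals):

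| *m* | PET item applied | PET item waived |
|---|---|---|
| 1 | 2/20 = 10% (1.2 to 31.7) | 3/20 = 15% (3.2 to 37.9) |
| 2 | 2/20 = 10% (1.2 to 31.7) | 4/20 = 20% (5.7 to 43.7) |
| 3 | 2/20 = 10% (1.2 to 31.7) | 5/20 = 25% (8.7 to 49.1) |
| 5 | 2/20 = 10% (1.2 to 31.7) | 7/20 = 35% |

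**Step 7. Baseline.** For aggressive lymphoma the response scan is PET/CT, but Sections 6.2 and 8.2 allow a CT baseline. Footnote 7 is attached to a calendar row that includes screening, so it could be read as asking for PET/CT at baseline too. The texts do not agree. The practical consequence is small: a follow-up PET can be called normal without an earlier one, but PET-negative PR needs an earlier positive PET.

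**The case against.** The best defense is that the PET item was plainly meant for patients assessed by PET. Section 12.1 says modality depends on subtype and expressly permits CT alone, and normalization presupposes an abnormal scan. On that view the defect is one missing qualifier. This is a fair account of the likely intent, but the qualifier is present on the marrow item and absent here, and CRu lists its exceptions without PET. The text still needs the sentence.

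A second defense is the central committee review of responses (Response Review, Section 16.1.2), which means the treating physician does not classify alone. That stands as a constraint. It does not settle the point, because the review confirms responses without setting a modality or a rule for an absent PET.

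Several stronger readings are tempting, and the documents do not support them:
- A reader might infer that the B-cell CR rate is uncertain by 30 to 50 points, taking 3 to 5 of 10 patients. Section 14.0 lists ORR, TTR, DOR and EFS for the subtype analyses, not the CR rate. That range also assumes that every indolent patient is followed by CT and resolves completely. The indolent CR rate in the lenalidomide background (Section 3.4) is 7% of 43 patients, on the single agent.
- A reader might infer that CT-only patients could reach CR on node size alone. The other items in Step 4 must also be met.
- A reader might infer that the date of CR biases the time-to-event endpoints. Neither TTR nor DOR is timed from CR.
- A reader might infer that CR cannot be judged in aggressive lymphoma without a baseline PET. Only PET-negative PR depends on an earlier scan, those patients already count as PR, and no endpoint counts them separately.

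**Conclusion.** The concern holds for indolent lymphomas assessed by CT alone. As written, the response definitions bar such a patient from CR and CRu even after complete resolution, and the plan does not say whether the PET item is waived. Each affected patient moves the pooled CR rate by 5 points of 20, with a matching opposite move in the PR rate where that patient would otherwise be PR. The total effect cannot be stated because the number of such patients is not given, and its direction depends on how the sites and the review committee handle the missing item.

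The effect is confined to a secondary, descriptive endpoint. The safety primary endpoint is untouched, and ORR, TTR and DOR are essentially so, on the assumption that a patient denied CR would still meet PR at the same assessment. CTCL skin response is scored by mSWAT and does not use the PET item. The change should be made because it is cheap and the rule as it stands gives a wrong category, but no main conclusion of the trial depends on it.

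**What to change.** 1. In the CR and CRu definitions of Section 12.1.1, state that the PET item applies whenever PET/CT is used for the response assessment, so that any PET-positive disease on treatment rules out CR and CRu. State that for indolent patients assessed by CT alone, CR and CRu are assigned on the remaining clinical, laboratory, size, organ and marrow items. Tying the item to the scan used, and not to a positive baseline PET, avoids exempting a patient whose on-treatment PET is positive.
2. In Section 12.1 and footnote 7 of Appendix G, require the modality for each indolent patient to be recorded at screening and kept for all response assessments.
3. In Section 14.0, report the CR rate by modality (CT-based and PET-based) alongside the pooled rate.
4. Reconcile Sections 6.2(g) and 8.2 item 9 with Section 12.1 and footnote 7 on the baseline scan for aggressive lymphomas, and say how PET-negative PR is handled when there is no earlier PET. A mandatory baseline PET/CT is not needed to resolve the main point.

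The cost is mostly protocol wording. Physicians lose the option to change modality mid-study, and the CR rate is split into small groups with wide intervals. For patients already assessed, items 1 and 3 can still be applied at analysis.
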